Efficacy of Er:YAG Laser in Decontamination of Dental Implants: An In-Vitro Study

Principal Investigator:

[name], D.M.D., Ph.D.

MS Student Co-Investigator:

[name], B.D.S.

Co-Investigators:

[name].

[name], D.D.S., M.S., Ph.D.

[name].

Study Location:

Tufts University School of Dental Medicine

[name]

[name]

NCT number: NCT03100435

Protocol Version Date:

Aug 10, 2017

I. Introduction

Key Question

Is Er:YAG laser a more effective method in decontamination of titanium surfaces compared to carbon fiber curettes?

Hypothesis

Er:YAG removes biofilm more effectively from titanium surfaces than carbon fiber curettes.

Aim

The aim of this study is to compare the amount of residual biofilm on titanium discs after decontamination with Er:YAG laser and carbon fiber curette.

Background and Rationale

Dental Implants

The American Association of Oral and Maxillofacial Surgeons estimated that 69% of adults ages 35 to 44 have lost at least one permanent tooth. The advent of oral implants has revolutionized dental practice and industry as a whole.¹ Implants provide a solution for tooth loss that is predictable with long-term success.¹ A success rate of 90% has been reported for both fully or partially edentulous restorations.²⁻⁵ Different implant systems have been developed with various sizes, shapes, surfaces, and prosthetic components.⁶ The success of dental implants depends on osseointegration, a concept defined as a direct structural connection at light microscopic level between the bone and surface of the implant.⁷ The dental implant and prosthetic market in the U.S is projected to reach \$6.4 billion by 2018.

Peri-Implantitis

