Studies evaluated efficiency of decontamination using scanning light microscopy, scanning electron microscopy (SEM), counting the colony forming units (CFU), bacterial smears, and photometric XTT–formazan evaluations.³¹ Molecular Probes' LIVE/DEAD® BacLight™ Bacterial Viability Kits provide a novel two-color fluorescence assay of bacterial viability that has proven useful for a diverse array of bacterial genera. LIVE/DEAD BacLight allow researchers to easily, reliably and quantitatively distinguish live and dead bacteria in minutes, even in a mixed population containing a range of bacterial types.

Since no consensus treatment for peri-implantitis has yet emerged, there is an urgent need for quantitative evaluation of the available treatment options. This study is designed to compare the biofilm removal efficiency of the Er:YAG laser with mechanical biofilm removal tools. Our goal is to establish whether Er:YAG laser significantly improves titanium surface decontamination. Our findings may contribute to the development of novel and efficient treatment of peri-implantitis.

Standard of Care in the TUSDM Periodontal Clinic

For patients who are experiencing a failing dental implant, the treatment starts with improving overall oral hygiene and controlling any etiological factors that prevent restoration of optimum oral health. The second step usually involves a surgical

intervention method such as open flap debridement, followed by implant decontamination using Er:YAG, titanium brushes, or plastic curettes. If the bony defect developed by the disease process is contained, bone regenerative therapy may be used.

I) Research Plan

A) Experimental Design

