This study is designed to investigate the efficiency of biofilm decontamination of Er:YAG laser compared to carbon fiber curette. The first phase is clinical wherein experimental subjects will be recruited. Full periodontal examination will be performed and alginate impressions will be taken. A custom mouth guard that holds multiple titanium discs will be fabricated. Experimental subjects will be instructed to wear this mouth guard for 72 hours, during which time a natural bacterial biofilm will form on the disc surfaces. The second phase of the study will be performed after collecting the discs from the subjects and exposing them *ex vivo* to one of four treatment groups 1) Er:YAG laser, 2) carbon fiber curette, 3) titanium brush, and 4) no treatment (control). The biofilm will be stained with LIVE/DEAD *BacLight* dye and the residual biofilm will be visualized under fluorescence microscopy. Quantification of residual biofilm will be performed using image analysis software (Image J, NIH). Statistical methods will be used to determine the significance of each treatment modality. The primary outcome of the study is the percent area of the titanium disc covered by biofilm.

B) Power Calculation

A power calculation was performed via the statistical software nQuery Advisor (Version 7.0). Using the results of Schwarz et al.⁴² for anticipated means and standard deviations, and assuming that the mean for the combination group is equal to the mean of the Er:YAG laser group, a sample of 8 subjects, allowing for ~20% dropout with a final projected sample size of 6 (8 discs per subject, 64 total discs) is sufficient for a Type I error rate of 5% and a power over 99%. Discs retrieved from each mouth guard will be randomized over the 4 treatment groups using the "sample" function of the statistical software package R (Version 3.1.2), so that each subject will contribute two discs to each treatment group.

C) Statistical analysis

Descriptive statistics (means, standard deviations, medians, and inter-quartile ranges) will be computed by group. Statistical significance will be assessed via repeated-measures ANOVA if the data are normally distributed, and Friedman's test if the data are not normally distributed. $P < 0.05$ will be considered statistically significant. The analysis will be conducted using SPSS Version 22.

D) Products

Titanium discs will be supplied by Straumann USA (Andover, MA).

E) Subject Characteristics

Inclusion criteria:

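### Section C states no test of the laser-versus-curette hypothesis and no rule for the other pairs; the four-group test it names can be significant because of the untreated control alone

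*Combined protocol and SAP*

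**What the plan says.** The Introduction sets a single comparison. The Key Question asks "Is Er:YAG laser a more effective method in decontamination of titanium surfaces compared to carbon fiber curettes", the Hypothesis is that "Er:YAG removes biofilm more effectively from titanium surfaces than carbon fiber curettes", and the Aim is to "compare the amount of residual biofilm on titanium discs after decontamination with Er:YAG laser and carbon fiber curette". Research Plan section A (Experimental Design) opens the same way: "This study is designed to investigate the efficiency of biofilm decontamination of Er:YAG laser compared to carbon fiber curette".

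Section A then lists four groups: laser, carbon fiber curette, titanium brush and an untreated control. Every subject contributes two discs to each group. The primary outcome is the percent area of the disc covered by biofilm.

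Section C (Statistical analysis) provides descriptive statistics by group and then one inferential rule: "Statistical significance will be assessed via repeated-measures ANOVA if the data are normally distributed", Friedman's test if they are not, and a threshold of P<0.05. It states no contrast, pairwise test or multiplicity rule.

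Two other sentences bear on intent. The Background says "This study is designed to compare the biofilm removal efficiency of the Er:YAG laser with mechanical biofilm removal tools", with tools in the plural. Section A says "Statistical methods will be used to determine the significance of each treatment modality". Neither says which comparisons will be tested, or how.

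Section B (Power Calculation) claims power over 99% at a 5% Type I error rate, with 8 subjects enrolled and 6 projected to complete. It does not name the comparison that has this power.

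**The concern.** With four groups, repeated-measures ANOVA and Friedman's test, in their usual overall form, ask whether any group differs from any other. Neither has a direction. An untreated control can be expected to carry more biofilm than any treated arm, so it can produce P<0.05 even if the laser and the curette perform identically. Such a result would not support the hypothesis.

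Repeated-measures ANOVA could carry a laser-curette contrast, but none is stated. Friedman's test supplies none.

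Two things are at stake. First, the study's only hypothesis has no prespecified test, so the form of that test and any adjustment could be chosen after the data are seen. Second, a power figure that refers to the overall test would say little about the question the study was set up to answer.

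**Working it through.** **Inputs from the documents.** Four groups; two discs per subject per group; 8 subjects enrolled, 6 projected; threshold 0.05; stated power over 99%.

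**The plan's own figure.** The stated power cannot be reproduced. The anticipated means and SDs are in a cited study and are not given in the protocol.

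**Assumptions for the checks.** The two discs are averaged to one value per subject and group. Gaps are in units of the within-subject SD of that value. Errors are normal with equal variances. All gap sizes are assumed.

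**1. Can the control alone make the overall ANOVA significant?** Set laser = curette = brush = 0 and control = d. The noncentrality is λ = n·Σ(μ − mean)², which here equals n·0.75·d², with 3 and 3(n−1) df.

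- n=6, d=2: λ = 6 × 0.75 × 4 = 18, with 3 and 15 df.

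| Control gap d | ANOVA, n=6 | ANOVA, n=8 | Friedman, n=6 | Friedman, n=8 |
|---|---|---|---|---|
| 1 SD | 32% | 44% | 21% | 32% |
| 2 SD | 89% | 97% | 71% | 89% |
| 3 SD | 99.9% | >99.9% | 96% | 99.8% |

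The Friedman figures are simulated with the chi-square reference. In the same setting a paired laser-curette t-test rejects in about 5%, its nominal rate.

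**2. An illustration that needs no SD.** Let the control rank worst in every subject and the three active arms tie on a mean rank of 2. Friedman's statistic is (12n/20) × [(4 − 2.5)² + 3 × (2 − 2.5)²] = (12n/20) × 3.

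- n=6: 3.6 × 3 = 10.8, P = 0.013.
- n=8: 4.8 × 3 = 14.4, P = 0.0024.

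**3. Does 99% overall power imply high power for the pair?** With no laser-curette difference at all, the overall ANOVA reaches 99% power at a control gap of 2.62 SD (n=6) or 2.18 SD (n=8). Paired-t power uses the noncentral t with n−1 df and noncentrality gap × √(n/2). At n=6 and a gap of 2 that is 2 × √3 = 3.46 on 5 df, giving 79%.

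Each setting below has 99% overall power at n=6, with laser equal to brush:

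| Curette worse by | Control worse by | Paired power for laser vs curette |
|---|---|---|
| 0.5 SD | 2.75 SD | 11% |
| 1 SD | 2.78 SD | 29% |
| 1.5 SD | 2.71 SD | 55% |
| 2 SD | 2.49 SD | 79% |
| 2.27 SD | 2.27 SD (curette as poor as control) | 88% |

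For 99% power on the pair itself, the paired test needs a gap of 3.17 SD at n=6 or 2.53 SD at n=8.

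**4. The other pairs.** Four groups give six pairs, so five remain after the primary. If all five were tested unadjusted at 0.05 and treated as independent, the family-wise error would be 1 − 0.95⁵ = 23%.

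**The case against.** The strongest reply is that the comparison itself is not missing. The Introduction fixes the pair, section A fixes the outcome and section C fixes the threshold. Group means and medians will be reported, so direction will be visible. The sentence on the significance of each modality suggests that treatment-level tests are intended. All of this stands, and it limits the concern to the missing test and the missing rule for the other pairs. A reader might infer that the plan leaves out the laser-curette comparison, or that it intends to present the overall P as proof of the laser's superiority. The documents support neither inference.

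The percentages also rest on assumed gaps. The first four settings in step 3 keep the laser-curette gap at 2 SD or less, which builds in modest pair power. The last row is kinder, at 88%. A reader might conclude that the study is underpowered for its hypothesis. That cannot be shown, because the means and SDs used in the power calculation are not in the documents.

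Finally, the choice of a paired t-test is partly preference. At n=6, a contrast with an error term from the three active arms holds 5% Type I error whether the control's SD is halved or doubled. It has 88% power at a 2-SD gap, given equal variances in the active arms. It does depend on the brush arm's variance.

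A block of text between the consent and subject-identification material was not available for review. Its neighbours do not concern analysis.

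**Conclusion.** The concern holds in this form: the hypothesis names a pair, and the plan states no test of that pair and no rule for the others. This conclusion follows from the text alone and needs no effect size.

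Its possible size is illustrated by the 2-SD control gap with identical active arms. There the overall test is significant in 89% (ANOVA) or 71% (Friedman) of trials at n=6, although the hypothesis is false. Those rates assume normal errors, equal variances and disc values averaged within subject and group.

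The stated power of over 99% is unassigned. If it describes the overall test, it does not carry over to the pair. What power the pair has cannot be determined from the documents.

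The documents do not show whether the data have already been analysed. The remedy has its full value only if it is adopted before that.

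**What to change.** **Section C.** Name one primary analysis: the within-subject difference, laser minus curette, in each subject's two-disc mean percent area. Test it two-sided at 0.05 and report an estimate with a 95% CI. A paired t-test serves, as does a within-subject contrast whose error term excludes the control. Name the Wilcoxon signed-rank test for the non-normal branch. The investigators should confirm that the curette pair alone is primary, since the Background speaks of tools in the plural.

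Keep the four-group test and the other five pairs as secondary, with a stated multiplicity adjustment. The choice of adjustment is open, but its limits should be checked. With Holm over five exact Wilcoxon tests, the smallest first-step adjusted p is 5 × 2/2ⁿ: 0.156 at n=6, 0.078 at n=7 and 0.039 at n=8. No secondary pair could reach 0.05 with 6 or 7 completers. The unadjusted primary Wilcoxon can, with a minimum p of 2/2⁶ = 0.031 at n=6.

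**Section B.** State which comparison the figure of over 99% refers to, and restate power for the primary contrast at 6 and 8 subjects.

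**Cost.** A few sentences and one recalculation, with no extra subjects or discs unless the restated power is judged too low. The paired test has 5 error df rather than 15 at n=6 (7 rather than 21 at n=8). At an assumed 2-SD gap with equal variances, its power is 79% against 90% for a contrast with the four-group pooled error at n=6, and 93% against 97% at n=8. The Wilcoxon option has 61% and 89%. In return, the paired test does not depend on the control's variance. At n=6 the pooled contrast's Type I error is about 1.6% if the control's SD is doubled and about 7.6% if it is halved.

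### An undefined normality check chooses between two four-group tests, and neither one tests laser against curette

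*Combined protocol and SAP*

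**What the plan says.** The Introduction states one hypothesis: the Er:YAG laser removes biofilm from titanium better than carbon fiber curettes. Experimental Design (section A) lists four arms (laser, curette, titanium brush, no treatment) and makes percent of disc area covered by biofilm the primary outcome.

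Statistical analysis (section C) assesses significance by "repeated-measures ANOVA if the data are normally distributed" and by "Friedman's test if the data are not normally distributed". P below 0.05 "will be considered statistically significant". The section names no normality test, cutoff or set of values to be checked (discs, subject means, differences or residuals). It names no pairwise comparison and no multiplicity adjustment for either branch.

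Power Calculation (section B) plans "a sample of 8 subjects, allowing for ~20% dropout with a final projected sample size of 6" and randomizes discs "so that each subject will contribute two discs to each treatment group". Neither section says how the two discs are combined. The sample is called "sufficient for a Type I error rate of 5% and a power over 99" per cent, without saying which test or contrast that power belongs to.

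**The concern.** Two things are left open that decide the primary result.

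First, the test is chosen from the data it is then applied to, by a check that is not defined. There are only 6 to 8 independent subjects. Percent area is bounded at 0 and 100, so skew near zero on well-cleaned discs is plausible. A check on so few values misses most skew, and its answer depends on which values are used. An analyst could settle that after seeing the data.

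Second, whichever branch is taken, the test asks whether the four arms are all alike. An untreated control is one of the four. If any cleaning method works, the overall test will tend to be significant whether or not laser beats curette. The pairwise test that would answer the hypothesis is left to be picked later, and the candidates differ a good deal in power at this sample size.

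**Working it through.** **Inputs from the plan.** Four arms (k = 4); 8 subjects enrolled and 6 projected; two discs per subject and arm; 5% level. No means, SDs or within-subject correlation are given: section B takes a cited study "for anticipated means and standard deviations" and proceeds by "assuming that the mean for the combination group is equal to the mean of the Er:YAG laser group", although no combination arm is among the four. All effect sizes and distributions below are therefore assumptions. Simulations use one value per subject and arm (the mean of two discs), and normal errors unless stated.

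**1. The plan's own figure.** The dropout step reproduces: 6 / (1 − 0.20) = 7.5, rounded up to 8. The power of over 99% cannot be reproduced without means and SDs. Working backwards, a repeated-measures ANOVA with 3 and 15 degrees of freedom (n = 6) reaches 99% at noncentrality 30.96. Spreading that same effect over different mean patterns gives, for laser versus curette by unadjusted paired t at n = 6:

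| Assumed pattern | Difference (residual SD) | ANOVA | Friedman | Paired t |
|---|---|---|---|---|
| Laser = brush, curette = control | 2.27 | 99% | 95% | 87% |
| Laser = brush, curette midway to control | 1.37 | 99% | 94% | 48% |
| Laser = brush, curette a quarter of the way | 0.69 | 99% | 92% | 17% |

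High power for the overall test says little about the contrast in the hypothesis.

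**2. The overall test does not answer the question.** Set laser, curette and brush equal and let only the control differ, by an assumed 3 residual SD. ANOVA and Friedman then reject 96% to 100% of the time at n = 6 and n = 8.

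**3. The normality check.** Shapiro-Wilk at 0.05, 4,000 runs per setting, independent values:

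| True shape | 6 values | 8 values | 24 values | 32 values |
|---|---|---|---|---|
| Lognormal, log-SD 0.5 | 13% | 19% | 62% | 75% |
| Exponential | 22% | 33% | 91% | 98% |
| Beta(2,8) | 8% | 11% | 34% | 48% |

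The number of checks matters too. Suppose each of the four arms is checked at n = 6 and any rejection leads to Friedman, treating arms as independent. Truly normal data then go to Friedman 1 − 0.95⁴ = 18.5% of the time, the lognormal 1 − 0.872⁴ = 42%, and the exponential 1 − 0.778⁴ = 63%. The wording of section C allows any of these readings.

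**4. Pairwise follow-up.** Assume a standardised paired difference of 1.5 between laser and curette, with the control well separated.

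- Paired t, n = 6: noncentrality 1.5 × √6 = 3.67, 5 degrees of freedom, critical value 2.571, power 83%. At n = 8: noncentrality 1.5 × √8 = 4.24, critical value 2.365, power 95%.
- Exact signed-rank, unadjusted: about 66% at n = 6 and about 92% at n = 8.
- Friedman rank comparison, unadjusted, n = 6: the standard error of a mean-rank difference is √(k(k+1)/(6n)) = √(20/36) = 0.745, so a gap of 1.96 × 0.745 = 1.46 is needed. Power is about 40% if the brush equals laser or curette, 56% if it lies midway between them, and 0% if it lies far outside them. In the last case laser and curette hold adjacent ranks; even if laser wins in all six subjects, z = 1/0.745 = 1.34 and P = 0.18.

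The smallest two-sided signed-rank P at n = 6 is 2/2⁶ = 0.031. Bonferroni needs 0.05/3 = 0.0167 for three pairs or 0.05/6 = 0.0083 for six, so an adjusted result is impossible. At n = 8 the minimum is 2/2⁸ = 0.0078, which passes both.

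**5. Type I error of the two-step rule.** Simulated with Shapiro-Wilk on residuals or per group, for normal, exponential and two lognormal shapes, n = 6 and 8, 4,000 runs each. The overall two-step test rejected a true null 4.1% to 5.7% of the time, against 3.3% to 5.1% for ANOVA alone and 3.5% to 4.6% for Friedman alone.

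**The case against.** The best defence is that the plan's fallback is the overall Friedman test and that this test is sound. It keeps 92% to 95% power at n = 6 where ANOVA has 99%, and about 99% at n = 8. That stands.

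Several stronger readings are tempting, and the documents do not support them:

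- *The Friedman branch can barely detect laser versus curette, or halves the power.* The rank comparison behind such figures is not in the plan, and its power depends on where the brush falls. An unadjusted signed-rank follow-up at n = 8 is close to the paired t-test.
- *The branch is chosen more or less by chance.* Rejection rates of 13% to 33% for those lognormal and exponential shapes mean that a single check on 6 to 8 values leads to ANOVA 67% to 87% of the time, and about 95% of the time for normal data.
- *The check uses 6 to 8 values.* The plan does not say so. On residuals or discs there would be more values and more power, although discs from one mouth are not independent.
- *The two-step rule inflates type I error.* No material inflation appeared in the settings tried.
- *Friedman cannot be run on two discs per arm.* It runs once the discs are averaged. The averaging is unstated for both branches, so this is a gap in wording and not a flaw of the fallback alone.

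The missing contrast is likewise common to both branches. None of this supplies a definition of the check or a test of the hypothesis.

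**Conclusion.** The point holds in this form. Section C leaves the primary test to an undefined check that has little power if run on subject-level values, and both tests it can choose address a question other than laser versus curette. The second part matters more and needs no distributional assumption: a four-arm test with an untreated control can be significant with no laser-curette difference.

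The size of the loss in follow-up is conditional. At n = 6 and an assumed standardised difference of 1.5 it runs from about 83% power (paired t) through 66% (signed-rank) to between 0% and 56% (rank comparison). At n = 8 the first two are about 95% and 92%. The one fixed limit is that with 6 subjects a signed-rank follow-up cannot survive Bonferroni over three or six pairs. The effect sizes, brush positions and skewed shapes are assumptions, because the plan gives no means or SDs.

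**What to change.** Replace the test-selection sentence in section C with wording to this effect:

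- The two discs per treatment are averaged within each subject.
- The primary analysis is a two-sided paired t-test at 0.05 of laser minus curette on these subject means, on the raw percent-area scale, whatever the shape of the data. Fix the raw scale in advance; a log scale fails if any mean coverage is 0%.
- The exact signed-rank P value for the same contrast is a sensitivity analysis only. Its minimum is 0.031 with 6 subjects and 2/2⁵ = 0.0625 with 5, so it should not carry the conclusion.
- The repeated-measures ANOVA across the four groups, and the comparisons involving brush and control, are kept as secondary.

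The cost is a short edit, with no extra subjects or discs. The data-driven switch is lost, and the t-test relies on approximate normality of 6 to 8 differences, which is why the signed-rank result is reported beside it. This is a cheap improvement.

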- Adults (18 years or older).
- Presence of enough teeth to support the mouth guard.
- English proficiency.
- Subjects diagnosed with clinical health, gingivitis, or slight chronic periodontitis defined as periodontal inflammation with slight (1-2mm) attachment loss. Subjects will not be stratified based on oral health.

Exclusion criteria:

- Subjects with insufficient dental support for the mouth guard
- Subjects diagnosed with moderate or severe chronic periodontitis.
- Subjects with known allergy to acrylic or titanium.
- Subjects who smoke cigarettes, cigars, snuff tobacco, or any other form of smoking.
- Subjects with a history of antibiotic treatment within the last six months.
- Subjects with contraindications to wearing a mouth guard, such as chronic obstructive pulmonary disease or severe sleep apnea.
- Subjects with uncontrolled or debilitating medical conditions, including but not limited to subjects with uncontrolled diabetes, hematologic disorders, cancers, immunosuppression, severe cardiovascular disease, or uncontrolled thyroid disease
- Subjects that are currently pregnant according to self-report as hormonal changes may affect the outcomes of the study.
- Subjects who are unable or unwilling to sign the informed consent form (ICF).
- Subjects may not participate in this study if they concurrently participate in another research study.

Subject withdrawal and termination criteria:

- Subject may withdraw from the study at any time. Subjects may remain patients of TUSDM if they decide to withdraw from the study.
- Investigators may terminate subjects if they no longer fulfill inclusion criteria, if an exclusion criterion is met, or if they do not show up for scheduled study visits. Subjects may remain patients of TUSDM if they are withdrawn from the study. If a subject withdraws from the study early and returns the mouth guard, the mouth guard and the titanium discs will not be analyzed and will be disposed of. Subjects withdrawing from the study early will not be eligible for the \$25 gift card.
- Unanticipated Adverse Device Event

The Principal Investigator will determine whether subjects (either withdrawn subjects or subjects completing the study) are in need of additional treatment and/or follow-up observation. Potential unforeseen adverse events may include allergic reaction to acrylic or titanium, or irritation of the gum by the mouth guard.

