measuring pocket depth, recession, attachment level, and bleeding on probing. If full periodontal examination was performed at TUSDM no more than 6 months ago, then existing records may be used to determine eligibility. As periodontal measurements are not a primary outcome, existing periodontal measurements collected by other TUSDM dentists may be used.

Inclusion and exclusion criteria will be considered and eligibility for the study will be determined.

Alginate impression for the maxillary teeth will be taken using stock plastic trays according to subject's arch size in conformance with standard of care practice.

After Visit 1 (In the Laboratory): Impression pouring, cast, and mouth guard fabrication

After the visit, alginate impressions will be disinfected and poured in the dental laboratory using dental stone. Subjects are not required to stay for the length of time of laboratory procedures. Dental stone will be allowed to set for 45 minutes before cast retrieval. After retrieval, casts will be trimmed according to laboratory standards. Titanium discs (5mm diameter, 1 mm thick, 4 discs each on the left and right premolar/molar areas, a total of 8 discs per subject, supplied by Straumann USA) will be fixed on the buccal surfaces of posterior teeth of the casts. A computerized positive pressure thermal-molding machine (Biostar, Great Lakes Orthodontics, Tonawanda, NY) will be used to fabricate a 1mm thick mouth guard on top of the cast, covering the attached titanium discs. The mouth guard will be removed from cast and trimmed to proper size. New titanium discs of the same size and count will be secured in mouth guard compartments with surgical adhesive (PeriAcryl, Salvin Dental Specialties, Charlotte, NC, Figure 1). The final shape of the appliance will resemble an occlusal mouth guard. The mouth guard will be disinfected in 0.12% chlorhexidine.

Figure 1: Gosau et al.⁴³

Visit 2: Within 2 months of Visit 1- Mouth guard delivery (approximately 60 minutes)

Medical history will be reviewed. Eligibility criteria will be re-evaluated. The mouth guard will be inserted into subject's mouth and adjusted for complete fitting and comfort. Intra-oral photograph will be taken in frontal view of the subject's teeth and gums while wearing the mouth guard.

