Subject will be asked to use the mouth guard for 72 hours continuously except during eating. Patient will be instructed to brush their teeth twice daily without the use of toothpaste and to floss once daily. Mouth rinses will be prohibited. These instructions will be given verbally with demonstration facing a mirror. The same instructions will be provided to study subjects in writing as well.

Visit 3: 3 days after Visit 2- Mouth guard retrieval (approximately 30 minutes)

Medical history will be reviewed. Eligibility criteria will be evaluated. Mouth guard will be retrieved from patient and stored until analysis.

After Visit 3(In the laboratory): Group Assigning, Experimental Treatments, and Measurements

After the visit, titanium discs will be separated from the mouth guard. Subjects are not required to stay for the length of time of laboratory procedures. Care will be taken not to disturb the surface biofilm. The back side of each disc will be numbered 1-64 and the subject and intraoral location will be recorded. Discs retrieved from each occlusal mouth guard will be randomized over the 4 treatment groups using the "sample" function of the statistical software package R (Version 3.1.2), so that each subject will contribute two discs to each treatment group.

After treatment, discs will be placed individually in a 24-well tissue culture plate, rinsed with saline and stained using the LIVE/DEAD BacLight dye Kit (Thermo Fisher Scientific, Waltham, MA). Equal volumes of Component A and Component B will be combined in a microfuge tube. The dye mixture will be added to the discs and incubated at room temperature in the dark for 15 minutes. The discs will be observed in a fluorescence microscope equipped with FITC/TRITC filter sets (Zeiss Axiovert 200, Carl Zeiss AG, Oberkochen, Germany). Percent biofilm covered area will be calculated with digital image analysis software (ImageJ, NIH).

Appointment Procedures	Visit 1 Screening/ Baseline	Visit 2 Baseline (Treatment Day 0)	Visit 3 Retrieval (Treatment Day 3)
Consent Form	X		
Demographics	X		
Medical/Dental History	X	X	X
Inclusion/Exclusion Criteria	X	X	X
Oral Examination	X		
Digital Photography		X	
Alginate Impressions	X		
Compensation			X

Mouth guard Delivery		X	
Mouth guard Instructions		X	
Mouth guard Retrieval			X

H) Subject Safety

1) Adverse Event Reporting

Adverse Events

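### The mouth guard is disinfected in chlorhexidine after the test discs are mounted, and no rinse before wear is specified, so residual antimicrobial on the discs cannot be excluded

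*Combined protocol and SAP*

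**What the plan says.** Section G, under the laboratory heading that follows Visit 1, gives the fabrication steps in sequence. Discs are placed on the cast, the guard is moulded over them, and it is removed and trimmed. Then: "New titanium discs of the same size and count will be secured in mouth guard compartments with surgical adhesive". After a sentence on the final shape of the appliance, the paragraph ends: "The mouth guard will be disinfected in 0.12% chlorhexidine".

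The next handling described is at Visit 2, which falls within 2 months of Visit 1: "The mouth guard will be inserted into subject's mouth and adjusted for complete fitting and comfort". The text gives no contact time, rinse, neutralisation, drying or storage between these two steps. The only rinse of the discs is with saline, after wear and after treatment.

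On the growth period, the experimental design (section A) says of the 72 hours of wear: "during which time a natural bacterial biofilm will form on the disc surfaces". Visit 2 adds: "Subject will be asked to use the mouth guard for 72 hours continuously except during eating". Other antimicrobial exposure is restricted. Section E excludes "Subjects with a history of antibiotic treatment within the last six months", and the Visit 2 instructions state "Mouth rinses will be prohibited". The primary outcome is the percentage of disc area covered by biofilm.

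**The concern.** The experiment needs a substrate: enough ordinary oral biofilm, grown in only three days, for a difference in removal to be visible. The protocol guards that substrate against antibiotics and rinses. Yet a technician who follows the fabrication steps in the order written would immerse the mounted test discs, and the compartments around them, in an antimicrobial before growth starts, with no instruction to remove it.

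If some activity persisted into wear, starting coverage would be lower or its composition atypical on every disc, controls included. Residual coverage after laser and after curette would both move towards zero, and the absolute difference between them would shrink. Uneven retention between compartments could add disc-to-disc noise. With 6 projected completers there is little reserve, and a null result could be read as equal instruments when there was too little biofilm to tell them apart. Coverage is not measured on treated discs before treatment, so the loss could not be corrected disc by disc.

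**Working it through.** **Order of steps.** As described: (1) guard trimmed; (2) new discs glued in; (3) finished shape described; (4) guard disinfected in chlorhexidine; (5) guard inserted at Visit 2; (6) 72 hours of wear; (7) discs removed and randomised, two per subject to each of four groups; (8) treatment; (9) saline rinse and staining. Disinfection follows mounting, and the only rinse comes at step 9. Randomisation at step 7 is within subject and after the exposure, so all four groups share it.

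**The plan's own figures.** The counts agree: 6 / (1 − 0.20) = 7.5, rounded up to 8 subjects; 8 × 8 = 64 discs. The stated power of over 99% cannot be reproduced, because section B takes its means and SDs from a cited study without giving the values. The effect of chlorhexidine on coverage is not given either. What follows is an illustration only.

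**Assumptions (none from the documents except n = 6 and the 5% level).** Untreated coverage is 60%; the laser removes 90% and the curette 60% of what is present; the SD of the paired difference is 10 points without carry-over; the test is a two-sided paired t-test, standing in for the laser–curette contrast.

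Let k be the fraction of normal coverage that forms.

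- Residual coverage: laser 60k × 0.10, curette 60k × 0.40.
- Difference: 24k − 6k = 18k points.
- Noncentrality: 18k × √6 / SD, on 5 degrees of freedom, critical value 2.571.
- At k = 1: 18 × 2.449 / 10 = 4.41, power 94%.

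The result depends on how the SD behaves as coverage falls, so three cases are shown: SD constant at 10, SD = 10√k, and SD = 10k.

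| Coverage formed | Laser vs curette residual | Difference | Power, SD constant | Power, SD ∝ √coverage | Power, SD ∝ coverage |
|---|---|---|---|---|---|
| 60% (k = 1) | 6% vs 24% | 18 | 94% | 94% | 94% |
| 45% (k = 0.75) | 4.5% vs 18% | 13.5 | 75% | 86% | 94% |
| 30% (k = 0.5) | 3% vs 12% | 9 | 43% | 70% | 94% |
| 15% (k = 0.25) | 1.5% vs 6% | 4.5 | 15% | 43% | 94% |

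**Cross-check from the plan's claimed power.** Take the four-group repeated-measures F test with 6 subjects, F(3, 15), and set the noncentrality to give exactly 99% power (30.96). If all group differences shrink by 10, 20, 30 or 50% with the SD fixed, power becomes about 97, 92, 83 or 52%. If the SD shrinks in proportion, power stays at 99%. The pattern is the same: there is a loss unless all of the noise scales with coverage.

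**The case against.** The strongest case against is that the protocol is silent on a rinse, which is not a decision to omit one. Its laboratory steps are brief throughout. The order is inferred from sentence sequence, and the disinfection sentence names the guard, not the discs. This stands as a limit on the claim: a rinse may be done in practice. It does not remove the point, because the paragraph is chronological and the sentence comes after the discs are in place.

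A reader might infer that chlorhexidine is in fact carried into the growth period, or that it is applied immediately before it. The documents support neither. Contact time and drying are not given. The interval from disinfection to insertion is unstated and could be weeks. The guard is then worn in saliva for 72 hours and taken out for meals. Nothing in the documents shows that activity persists.

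A reader might also infer that the comparison of laser with curette is biased, or that the protocol contradicts its own ban on rinses. It is not biased, since the exposure is common to all discs in a guard and allocation follows it. Nor is there a contradiction: a ban on rinses during growth concerns a different exposure from one disinfection before wear. The two merely sit awkwardly together.

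The untreated discs come from the same guards and would show low coverage, so a lack of biofilm need not go unnoticed. That too stands, but these discs could not identify the cause or restore the lost contrast.

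Finally, the loss of power depends on the SD assumption, and on a scale bounded at zero some shrinkage of the SD is to be expected. The constant-SD column should therefore be read as the pessimistic end of the range.

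**Conclusion.** The point holds as a risk that the plan leaves open: disinfection is described after disc mounting, no rinse before wear is specified, and residual antimicrobial on the test surfaces cannot be excluded. The effect would be non-differential, reducing or altering the biofilm in every group.

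Its size cannot be taken from the documents and may be nil. Under the stated assumptions, halved coverage would leave power between 43% and 94%, depending on how far the SD falls with coverage; with no carry-over, nothing is lost. This is an inexpensive improvement to the procedure, not a demonstrated flaw in the comparison.

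**What to change.** In the laboratory steps after Visit 1, reverse the order: disinfect the trimmed guard, rinse it thoroughly with sterile saline or water, and then secure clean discs in it. If the finished appliance must be disinfected, add a sterile saline rinse of guard and discs before delivery at Visit 2. If the laboratory already rinses, the protocol should say so.

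Disinfection of the appliance is kept, and neither the sample size nor the analysis changes. The cost is a few minutes for each of eight guards, and discs have to be mounted under clean conditions.
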